### 1.3. Sample Size and Power

Sample sizes for GS-9876 and placebo groups are determined based on the superiority test of 1 dose of GS-9876 compared to placebo based on the change from baseline in DAS28(CRP) at Week 12. When assuming a difference of 1.2 between the 2 groups and a common standard deviation of 1.35, 20 subjects in each of the GS-9876 groups and 20 in the placebo group are required to obtain 78% power at a 2-sided 0.05-level. **PPD**

. Therefore, the total sample size will be 80 (20 per treatment group).

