#### **3.7.2. Analysis Visit Windows**

Subject visits may occur on days not specified in the protocol (eg, unscheduled visits). Therefore, for the purpose of analysis, observations will be assigned to analysis windows.

In general, the baseline value will be the last nonmissing value on or prior to the first dose date of study drug.

**Table 3-1 Analysis Visit Windows for Joint Count Assessment, HAQ-DI, PhGA, PtGA, and On-Treatment CRP, Safety Laboratory Data, Weight, Vital Signs, ECG**

Nominal Visit	Nominal Study Day	Lower Limit	Upper Limit
Baseline	1	(none)	1
Week 2	15	2	22
Week 4	29	23	43
Week 8	57	44	71
Week 12	85	72	≥ 85

The analysis windows for joint count assessment, health assessment questionnaire - disability index (HAQ-DI) (including the patient’s assessment of pain), physician’s global assessment of disease activity (PhGA), patient’s global assessment of disease activity (PtGA), on-treatment CRP, safety laboratory, weight, vital signs and electrocardiogram (ECG) are provided in [Table 3-1](#). CRP, safety laboratory, weight, vital signs, and ECG data collected up to the last dose date of any study drug + 3 days are considered to be on-treatment data.

CRP, safety laboratory, weight, vital signs, and ECG data collected after last dose date of any study drug + 3 days will be considered as posttreatment data and will be summarized up to last dose date plus 30 days, and labeled as “FU-Week 4”. Data obtained after last dose date plus 30 days will be excluded from the summaries, but will be included in the listings.

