### **6.2.3. Analysis of the Primary Efficacy Endpoint**

Change from baseline in DAS28(CRP) at Week 12 will be analyzed using a mixed-effects model for repeated measures (MMRM) approach. The model will include the fixed effects of treatment, visit, treatment by visit interaction, and baseline DAS28(CRP) value. Subjects will be included as a random effect. Missing change scores (eg, due to early withdrawal, etc.) will not be otherwise imputed using the MMRM approach. An unstructured variance-covariance matrix for the repeated measures and Kenward-Roger approximation for the denominator degrees of freedom will be used in the mixed-effects model.

From the MMRM approach, estimated differences in mean change from baseline between each of the GS-9876 doses and the placebo group will be presented with 95% confidence intervals (CIs) and p-values. **PPD**

Change from baseline in DAS28(CRP) will be summarized by treatment and visit using descriptive statistics (sample size, mean, SD, median, Q1, Q3, minimum, and maximum). Plots of mean  $\pm$  SD of DAS28(CRP) values and changes from baseline in DAS28(CRP) over time will be presented.

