#### 6.3.2. Analysis Methods for Secondary Efficacy Endpoints

The ACR20 response rates at Week 12 between each of the GS-9876 dosed groups and the placebo group will be compared using a stratified Cochran-Mantel-Haenszel (CMH) chi-square test adjusting for stratification factors in randomization (ie, prior inadequate response to biologic

therapy, yes vs. no; and Geographic region, region 1 vs. region 2 as defined in Section 3.3). The difference in response rates between treatment groups and the corresponding 95% CIs will be presented. The CMH chi-square p-value for testing the superiority of each of the GS-9876 doses as compared to placebo will be provided, as well as the 2-sided 95% exact CI of the ACR20 response rate based on Clopper-Pearson method for each treatment group. Subjects who do not have sufficient measurements to establish efficacy at Week 12 will be considered as failures (ie, non-responder imputation [NRI]). Sensitivity analysis will be conducted by imputing missing components for determining ACR20 as well as early dropouts via the last observation carried forward (LOCF) method.

[figure not shown]
For ACR50 and ACR70 at Week 12, the same CMH approach with NRI as in the analysis of ACR20 described above will be adopted.

The difference in change from baseline in HAQ-DI between each of the GS-9876 dosed groups and the placebo group will be analyzed using a similar MMRM approach as described in Section 6.2.3. The model will include the fixed effects of treatment, visit, treatment by visit interaction, and baseline value. Subjects will be included as a random effect. Missing change scores (eg, due to early withdrawal, etc) will not be otherwise imputed using the MMRM approach.

[figure not shown]
Mean ACR 20/50/70 response rates with NRI will be plotted by treatment and visit. Mean  $\pm$  SD over time will be plotted for each component of ACR 20/50/70.

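### Does a random subject effect beside an unstructured covariance matrix undermine the primary MMRM and its Kenward-Roger inference?

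*SAP*

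**What the plan says.** Section 6.2.3 of the SAP states: "Change from baseline in DAS28(CRP) at Week 12 will be analyzed using a mixed-effects model for repeated measures (MMRM) approach". On the mean structure it says: "The model will include the fixed effects of treatment, visit, treatment by visit interaction, and baseline DAS28(CRP) value". The next sentence is "Subjects will be included as a random effect". Two sentences later comes the covariance: "An unstructured variance-covariance matrix for the repeated measures and Kenward-Roger approximation for the denominator degrees of freedom will be used in the mixed-effects model".

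The section does not mention a random intercept, gives no structure for a random-effects covariance and shows no code. It names no alternative structure in case the unstructured matrix fails to converge.

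Section 6.3.2 has HAQ-DI "analyzed using a similar MMRM approach as described in Section 6.2.3". It repeats the sentence on subjects as a random effect but does not restate the unstructured matrix or Kenward-Roger.

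**The concern.** In a mixed model, a random subject effect normally means a variance component that adds the same constant to every within-subject variance and covariance. An unstructured matrix already leaves each of those entries free. Specifying both asks the data to separate two things that they cannot separate: the likelihood is flat along one direction and the information matrix of the covariance parameters is singular. Kenward-Roger uses the inverse of that information matrix, so it is natural to suspect the degrees of freedom and adjusted standard errors too.

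The affected model is the only planned analysis of the primary endpoint, since Section 6.2.4 rules out sensitivity analyses. If the literal model stopped with an error, or gave p-values that depended on how the software treats the surplus parameter, someone would have to choose a repair after unblinding.

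**Working it through.** **Inputs from the SAP**
- Post-baseline visits: Weeks 2, 4, 8 and 12 (Section 3.7.2, Table 3-1), so T = 4.
- 20 subjects in each of four arms, difference 1.2, SD 1.35, two-sided 0.05, stated power 78% (Section 1.3).

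**Assumptions, for the numerical illustration only**
- SDs of change of 0.8, 0.9, 1 and 1 times 1.35 at the four visits.
- Correlation 0.4 + 0.6 × 0.5^(0.6 × lag): from 0.80 at lag 1 to 0.57 at lag 3.
- Dropout of about 4% per visit interval.

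**The plan's own figure.** The noncentrality is 1.2 / (1.35 × √(2/20)) = 1.2 / 0.4269 = 2.811. With 38 df the noncentral t gives power 78.2%, which reproduces 78%. This calculation uses only the Week 12 SD, so the present point does not affect it.

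**Step 1: the redundancy is real under the literal reading.** Write V = sJ + R, where s is the subject variance, J the 4 × 4 matrix of ones and R unstructured. R has 4 × 5 / 2 = 10 parameters. J is itself a symmetric 4 × 4 matrix, so it lies in the space that R spans. That gives 11 parameters and information of rank 10. In the simulated data the smallest eigenvalue of the information matrix is 2.55 with R alone and about 3 × 10⁻¹⁴ with s added.

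**Step 2: the fitted V does not change.** Every positive definite V is reached with s = 0. Adding s > 0 to a positive definite R again gives a positive definite V. Both forms therefore allow the same set of V and have the same REML maximum. Moving along the flat direction in the simulated data, with R = V − sJ:

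| s | smallest eigenvalue of R | REML log-likelihood |
|---|---|---|
| 0 | 0.209 | −107.4105 |
| 0.1 | 0.207 | −107.4105 |
| 0.3 | 0.203 | −107.4105 |
| 0.5 | 0.195 | −107.4105 |

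**Step 3: Kenward-Roger does not change.** Let the 10 entries of V be Aθ, with θ the 11 parameters and A a 10 × 11 matrix of full row rank.
- The information for θ is A′IA, where I is the 10 × 10 information for V.
- For any generalized inverse W of A′IA, AWA′ = I⁻¹.
- V is linear in the parameters in both forms, so the second-derivative term of the Kenward-Roger adjustment is zero in both.
- The remaining adjustment to the variance of the fixed effects uses W only through AWA′.
- For one contrast c, with v its model-based variance and g the gradient of v, df = 2v² / (g′Wg). This also uses W only through AWA′.

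Standard error and df are therefore the same as with the unstructured matrix alone. Setting s to 0 gives the same result directly.

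**Step 4: numerical confirmation.** These are Week 12 contrasts against the reference arm in the simulated trial.

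| Contrast | Covariance model | Estimate | Kenward-Roger SE | df | p |
|---|---|---|---|---|---|
| 1 | unstructured only | −1.4806 | 0.4330 | 72.58 | 0.00103 |
| 1 | unstructured + subject effect | −1.4806 | 0.4330 | 72.58 | 0.00103 |
| 2 | unstructured only | −0.6334 | 0.4314 | 71.80 | 0.146 |
| 2 | unstructured + subject effect | −0.6334 | 0.4314 | 71.80 | 0.146 |

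Agreement holds to eight decimals for estimate and SE and six for df. The values depend on the simulated data; the equality follows from Steps 2 and 3 and does not.

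**The case for a change.** The best argument for a change is that repairs are not all equivalent. An analyst who meets a singular-Hessian message could drop the unstructured matrix and keep the subject effect, which leaves compound symmetry with one pooled variance over visits. Take assumed SDs of change of 0.90, 1.05, 1.20 and 1.35, complete data and no baseline adjustment:
- The pooled SD is √(5.175/4) = 1.137.
- The Week 12 contrast SE is 1.137 × √(2/20) = 0.360, against 1.35 × √(2/20) = 0.427, a ratio of 0.84.
- The critical value 1.96 then acts like 1.96 × 0.84 = 1.65, so a nominal 5% test has a type I error of about 10%.
- With equal SDs at all visits the ratio is 1 and there is no inflation.

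The arithmetic stands, but it describes a different model. The SAP fixes the unstructured matrix in explicit words, so discarding it would depart from the plan, and Section 1 requires changes made after finalization to be documented in the study report. Within the model that the SAP specifies, no choice alters the primary result.

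Two smaller points stand in part. First, Section 6.3.2 is less explicit for HAQ-DI and could be read as a random-intercept model. But it refers back to Section 6.2.3, and carrying over that section's covariance and degrees of freedom is the ordinary reading. Second, no fallback structure is named. That matters if the unstructured matrix itself fails to converge, which is a separate question that removing the subject sentence would not answer.

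The rewording would cost almost nothing, but low cost is not a gain when no estimate, interval or p-value changes.

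**Conclusion.** The concern is right about the algebra and wrong about the consequence. If the sentence means a separate variance component, that component cannot be estimated beside an unstructured matrix, and a literal fit may produce a warning. The effect on the estimates, Kenward-Roger standard errors, degrees of freedom, p-values and the 78% power is nil. This rests on two conditions: the unstructured matrix is kept, as Section 6.2.3 requires, and the surplus parameter is handled by a generalized inverse or set to zero.

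The literal reading is also not the only one. In a model called an MMRM, with the unstructured matrix placed on the repeated measures and no other variance component described, the sentence serves equally well to identify the subject as the unit within which measurements are correlated. An analyst would code it that way and obtain the standard model. This is loose wording that is resolved sensibly in programming, and it needs no change to the plan.

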### **6.2.4. Sensitivity Analysis of the Primary Efficacy Endpoints**

Sensitivity analyses of the primary efficacy endpoint will not be performed.

### **6.2.5. Subgroup Analysis of the Primary Efficacy Endpoint**

Subgroup analysis will be performed for the primary efficacy endpoint for the subgroups outlined in Section 3.4. The difference between treatment groups and the corresponding 95% CIs will be presented.

## **6.3. Secondary Efficacy Endpoints**

The secondary efficacy endpoints are:

- The proportion of subjects who achieve ACR 20/50/70 at Week 12
- Change from baseline in HAQ-DI score at Week 12

### **6.3.1. Definition of Secondary Efficacy Endpoints**

#### **6.3.1.1. ACR 20/50/70**

A subject achieves ACR20 response when this subject has

- $\geq 20\%$  improvement from baseline in the tender joint count (TJC68), AND
- $\geq 20\%$  improvement from baseline in the swollen joint count (SJC66), AND

- $\geq 20\%$  improvement from baseline in at least 3 of the following 5 items:
  - 1) Physician's Global Assessment of Disease Activity (PhGA),
  - 2) Patient's Global Assessment of Disease Activity (PtGA),
  - 3) Patient's pain assessment,
  - 4) Patient's assessment of physical function (HAQ-DI) score,
  - 5) C-reactive protein (CRP)

Percent improvement from baseline at a post-baseline visit is calculated as follows for all 7 components mentioned above:

$$([\text{baseline value} - \text{post-baseline value}] / \text{baseline value}) * 100\%$$

If the baseline value is 0 and the post-baseline value is also 0, then the percent improvement from baseline is set to 0. If the baseline value is 0 and the post-baseline value is non-zero then the percent improvement from baseline is set to missing.

In the case that some ACR20 components are missing, the ACR20 assessment will be derived based on the non-missing components. If non-missing components are not sufficient to determine ACR20 response, then the ACR20 response will be considered as missing.

ACR50 and ACR70 are similarly defined as ACR20 above, except the improvement threshold from baseline is 50% and 70%, respectively.

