## 6. EFFICACY ANALYSES

### 6.1. General Considerations

The primary analysis set for efficacy analyses will be the FAS, defined in Section 3.1.2.

If multiple valid, nonmissing efficacy measurements exist in an analysis window, records will be chosen based on the following rules if a single value is needed:

- If record collection date/time is known, latest record will be taken
- If time is unknown, the worst scenario will be selected

For the composite endpoints including DAS28(CRP), ACR 20/50/70, SDAI, and CDAI, we use the following steps unless otherwise specified:

- Step 1: Put each component value into a visit window
- Step 2: Within each visit window, select the component data point for analysis
- Step 3: Combine these selected data points within each visit window across the components.

Below are the descriptions for the imputation methods that will be used throughout the efficacy analyses:

- Observed case (OC): missing values remain missing. For the above composite endpoints, in the case that some components are missing, the composite endpoint assessment will be derived based on the non-missing components. If non-missing components are not sufficient to determine final composite endpoint, then the composite endpoint will be considered as missing.
- Last observation carried forward (LOCF): For the above composite endpoints, First LOCF all components over all visits, then combine the components as mentioned above.
- Non-responder imputation (NRI): For all binary response measurements, starting from OC, all missings will be treated as non-responders.

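### An ACR component that rises from 0 is set to missing, so some certain non-responders become undetermined and can drop out of the ACR20 LOCF sensitivity analysis

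*SAP*

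**What the plan says.** SAP Section 6.3.1.1 requires at least 20% improvement in TJC68 and in SJC66 for ACR20, and also "improvement from baseline in at least 3 of the following 5 items": physician global, patient global, pain, HAQ-DI and CRP. One percent-improvement formula, with the baseline value as divisor, serves all seven components. ACR50 and ACR70 differ only in the threshold.

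Two rules cover a zero baseline:

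- No change from 0: "If the baseline value is 0 and the post-baseline value is also 0, then the percent improvement from baseline is set to 0".
- A rise from 0: "If the baseline value is 0 and the post-baseline value is non-zero then the percent improvement from baseline is set to missing".

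The response is then derived from the components that are not missing, with this fallback: "If non-missing components are not sufficient to determine ACR20 response, then the ACR20 response will be considered as missing".

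Three further statements decide what happens to a missing response:

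- Section 6.3.2, main ACR analysis (NRI): "Subjects who do not have sufficient measurements to establish efficacy at Week 12 will be considered as failures".
- Section 6.1, definition of NRI for binary measures: "starting from OC, all missings will be treated as non-responders". OC is the observed-case data set.
- Section 6.3.2, ACR20 sensitivity analysis: "Sensitivity analysis will be conducted by imputing missing components for determining ACR20 as well as early dropouts via the last observation carried forward". For composite endpoints, Section 6.1 has the components carried forward first and combined afterwards.

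**The concern.** None of the seven components can fall below 0: they are joint counts, 0-100 visual analog scales, a 0-3 disability index and a serum concentration. A component that is 0 at baseline can therefore only stay at 0 or worsen, and in neither case can it reach a 20%, 50% or 70% improvement. The SAP treats the milder outcome (0 to 0) as a known failure and the worse one (0 to non-zero) as unknown. Dividing by zero leaves the percentage undefined, but whether the criterion is met is still known.

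At stake is the only ACR20 sensitivity analysis visible in the SAP. Its purpose is to show whether the handling of missing data matters. If it loses subjects whose data are complete and who are known failures, it can differ from the NRI result for a reason unrelated to missing data.

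**Working it through.** The SAP states no figure for this rule, so there is none to reproduce. The check enumerates the possible patterns and then illustrates the size.

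**1. One of the five items goes from 0 to non-zero.** Six components remain (TJC68, SJC66 and four items), each improved or not, giving 2^6 = 64 patterns. ACR20 counts as determined only if it comes out the same whether the missing item is filled in as improved or as not improved.

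- TJC68 or SJC66 not improved: non-responder under either coding. 48 patterns.
- Both joint counts improved, 0 or 1 of the four items improved: at most 2 of 5, so non-responder under either coding. 1 + 4 = 5 patterns.
- Both improved, exactly 2 of the four improved: the SAP rule leaves 2 or 3 of 5, hence missing. The true count is 2 of 5, a non-responder. C(4,2) = 6 patterns.
- Both improved, 3 or 4 of the four improved: responder under either coding. 4 + 1 = 5 patterns.

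Total: 48 + 5 + 6 + 5 = 64. The codings differ in 6 of 64. The joint-count condition matters: exactly 2 of the four items are improved in 6 × 4 = 24 patterns, and in 18 of these a failed joint count already settles the response.

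**2. A joint count itself goes from 0 to non-zero.** The other joint count and the five items again give 64 patterns. The response becomes missing when the other joint count improved and at least 3 of 5 items improved: C(5,3) + C(5,4) + C(5,5) = 10 + 5 + 1 = 16 of 64. In truth all 16 are non-responders, because both joint counts are mandatory.

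These counts show where the rule misclassifies. They are not probabilities, since the patterns are not equally likely.

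**3. NRI.** A response that is missing in the observed-case data becomes a non-response. The affected subjects are counted correctly, so the ACR20, ACR50 and ACR70 results do not change.

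**4. LOCF.** Take baseline 0 and a Week 12 value of 5.

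- LOCF on component values, as Section 6.1 most naturally reads: Week 12 is observed, so nothing is carried forward, and the percent improvement is missing whatever the earlier visits showed.
- LOCF on percent improvement: an earlier post-baseline value of 0 carries 0% forward and the subject is a non-responder. If every post-baseline value is non-zero, the result stays missing (unless the baseline visit itself were carried forward).

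**5. Size, if such subjects leave the denominator.** The 20 per arm is from Section 1.3; the responder counts r are assumed. With k known non-responders lost, the arm's rate moves from r/20 to r/(20 − k).

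| r | r/20 | k = 1 | k = 2 |
|---|---|---|---|
| 4 | 20.0% | 4/19 = 21.1% | 4/18 = 22.2% |
| 8 | 40.0% | 8/19 = 42.1% | 8/18 = 44.4% |
| 12 | 60.0% | 12/19 = 63.2% | 12/18 = 66.7% |

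One lost subject raises the arm's rate by 1.1, 2.1 or 3.2 percentage points.

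**The case against.** The strongest objection is that the SAP nowhere says a subject still undetermined after LOCF is excluded. In Section 6.3.2 the sentence counting subjects without sufficient measurements as failures stands directly before the LOCF sentence, in the same paragraph, and Section 6.1 describes NRI as covering all binary measures. A programmer could apply LOCF and count the remainder as failures, and the effect would vanish. This stands in part: exclusion is inferred. It is still the more natural reading, because NRI is defined from the observed-case data, the failure sentence carries the NRI label, and the affected subjects do not lack measurements.

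Second, percent change from 0 is undefined, so setting it to missing is a familiar arithmetic convention. That holds for summarising the percentage. It does not hold for deciding whether a threshold was met.

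Third, the reach is narrow. A subject needs a baseline component of exactly 0 despite active RA, a rise in it by Week 12, and a borderline pattern in the rest. Zero joint counts at baseline are unlikely, and Section 3.6 sets values below the quantitation limit just under that limit for descriptive statistics, so a CRP of 0 is also unlikely. HAQ-DI, pain or a global score are the realistic candidates. All of this stands.

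A reader might infer that the planned ACR results, or the comparison with placebo, are biased. The SAP does not support that: the NRI results are unchanged, LOCF is stated for ACR20 only, and nothing suggests that zero baselines differ between arms.

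**Conclusion.** The point holds as a minor defect. The rule labels some certain non-responders as undetermined: 6 of 64 patterns when one of the five items rises from 0, and 16 of 64 when a joint count does. The NRI analyses are unaffected, and the primary endpoint does not use percent improvement.

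The only exposed analysis is the ACR20 LOCF sensitivity analysis. There a known failure can leave the denominator, and the affected arm's rate can only go up. The 1 to 3 points per lost subject rests on three assumptions: LOCF acts on component values, a response still missing after LOCF is excluded, and an arm of 20 has 4 to 12 responders. The SAP gives no frequency of zero baselines, so the expected effect cannot be quantified; it is probably small. This is a desirable correction, not a necessary one.

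**What to change.** In Section 6.3.1.1, replace the sentence on a rise from 0 with wording such as: if a component is 0 at baseline and non-zero after baseline, it is counted as not improved (criterion not met) for ACR20, ACR50 and ACR70, and this includes TJC68 and SJC66.

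With that coding every pattern enumerated above is determined, and the order in which LOCF is programmed no longer matters for these subjects. As an optional addition, Section 6.3.2 could say how an ACR20 response still missing after LOCF for any other reason is counted.

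The cost is one sentence in the SAP and a small change to the derivation program. No new data are needed and the NRI results stay the same.
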